9.4 Analysis of Vital Signs

Vital sign measurements of systolic and diastolic blood pressure, pulse rate, body temperature, and weight will be summarized.

For the analysis of vital sign data, values observed up to 30 days after the last dose of study drug will be included.

Each vital sign variable will be summarized for all time points (starting with Baseline) with the number of non-missing observations, mean and standard deviation, median, minimum and maximum.

For continued groups, mean change from baseline to each applicable post-baseline visit will be summarized for each vital sign variable, with the number of observations, baseline mean, and visit mean. The change from baseline mean, standard error, and 95% confidence interval will be presented for the mean change from baseline within each treatment group and difference between treatment groups.

Vital sign variables will be evaluated based on potentially clinically important (PCI) criteria ([Appendix C](#)). For each vital sign PCI criterion, the number and percentage of subjects who have a vital sign value meeting the criteria will be summarized. Listings

will be provided to summarize subject-level vital sign data for subjects meeting PCI criteria.

9.5 Safety Subgroup Analyses

No planned safety subgroup analyses.

9.6 Other Safety Analyses

ECG is collected at Screening and Weeks 2, 4, 8, 12, 16, 20, 24 and 48. The number and percentage of subjects with QTcF prolongation (QTcF > 500 msec) will be summarized by treatment groups using Safety Analysis Set population.

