5.5 Withdrawal of Subjects and Discontinuation of Study

Subjects can request to be discontinued from participating in the study at any time for any reason including but not limited to disease progression or lack of response to treatment. The Investigator may discontinue any subject's study treatment at any time for any reason, including but not limited to disease progression, lack of response to treatment, safety concerns, or failure to comply with the protocol. See Section 6.2 on Toxicity Management for toxicity management criteria.

At Week 24, the Investigator must assess and document in source if continuing in the study is in the best interest of the subject.

Subjects will be discontinued from study drug immediately if any of the following occur:

- Development or worsening of lupus manifestation requiring introduction of certain prohibited medications or dosages when continuation of the study drug would place the subject at risk, as determined by the AbbVie TA MD. The following will require discontinuation of study drug immediately:
 - Cyclophosphamide
 - Belimumab
 - Rituximab
 - More than one of the following in combination: azathioprine, mycophenolate, leflunomide, MTX, cyclosporine, or tacrolimus;
 - Plasmapheresis
 - High-dose corticosteroids (≥ 60 mg prednisone equivalent oral or parenteral)
 - IVIG
- Clinically significant abnormal laboratory results or AEs, which rule out continuation of the study drug, as determined by the investigator or the AbbVie TA MD.
- Serious infections (e.g., pneumonia, sepsis) which cannot be adequately controlled by anti-infective treatment or would put the subject at risk for continued participation in the trial, as determined by the Investigator or the AbbVie TA MD.
- The Investigator believes it is in the best interest of the subject.
- The subject requests withdrawal from study drug or the study, or the Sponsor decides to discontinue 1 or more treatment groups after the interim analysis.
- Inclusion or exclusion criteria violation was noted after the subject started study drug, when continuation of the study drug would place the subject at risk as determined by the AbbVie TA MD.
- Subject develops an ECG change considered clinically significant and with reasonable possibility of relationship to study drug or a confirmed absolute QTcF value > 500 msec or confirmed increase of ≥ 60 msec from Baseline.

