 - Subject's QTcF increases from Baseline ≥ 60 msec, the investigator will evaluate, confirm the value, and treatment should be stopped.
- Subject develops active or latent TB at any time during the study.
- The subject becomes pregnant while on study drug.
- Malignancy, except for localized NMSC or CIS of the cervix.
- Subject is significantly non-compliant with study procedures, including inconsistent study drug dosing, which would put the subject at risk for continued participation in the trial as determined by the Investigator or the AbbVie TA MD.
- Subject develops a GI perforation.
- If a diagnosis of deep vein thrombosis, pulmonary embolus, or non-cardiac, non-neurologic arterial thrombosis is confirmed.

- Subject develops active neuropsychiatric SLE (excluding lupus headache) as defined by the CNS portion of SLEDAI-2K or BILAG.
- Subject develops Class IV lupus nephritis (confirmed by biopsy).

In order to minimize missing data for efficacy and safety assessments, subjects who prematurely discontinue study drug treatment should:

- Continue in the study without receiving study drug
- Have all procedures performed outlined in the Premature Discontinuation (PD) visit, preferably within 2 weeks of study drug discontinuation
- Continue with their regular study visit schedule

No PK or biomarker samples should be collected after the PD visit.

For subjects to be considered lost to follow-up, reasonable attempts must be made to obtain information on the subject's final status. At a minimum, 2 telephone calls must be made and 1 certified letter must be sent and documented in the subject's source documentation.

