Subjects must be discontinued from study drug for an ECG change considered clinically significant and with reasonable possibility of relationship to study drug OR a confirmed absolute Fridericia's correction formula (QTcF) value > 500 msec or confirmed increase of ≥ 60 msec from Baseline.

Management of Muscle-Related Symptoms

If a subject experiences symptoms suggestive of myositis or rhabdomyolysis, CPK and aldolase measurements should be requested and will be provided after review by the TA MD with clinical management and/or study drug interruption as deemed appropriate by the treating physician. Please refer to [Table 4](#) below for further instructions.

Management of Thrombosis Events

Subjects who develop symptoms of thrombosis should be promptly evaluated and treated appropriately. If the diagnosis of deep vein thrombosis, pulmonary embolus, or non-cardiac, non-neurologic arterial thrombosis is confirmed, the subject must be discontinued from study drug.

Management of Select Laboratory Abnormalities

For any given laboratory abnormality, the investigator should assess the subject and apply the standard of care for medical evaluation and treatment following any local guidelines. Specific toxicity management guidelines for abnormal laboratory values are described in [Table 4](#) and may require a supplemental eCRF to be completed (see Section 6.1 Complaints and Adverse Events). All abnormal laboratory tests that are considered clinically significant by the investigator will be followed to a satisfactory resolution. If a repeat test is required per [Table 4](#), the repeat testing must occur as soon as possible.

Table 4. Specific Toxicity Management Guidelines for Abnormal Laboratory Values

Laboratory Parameters	Toxicity Management Guidelines
Hemoglobin	
 • If hemoglobin < 8 g/dL interrupt study drug dosing and confirm by repeat testing with a new sample. • If hemoglobin decreases ≥ 3.0 g/dL from baseline without an alternative etiology, interrupt study drug dosing and confirm by repeat testing with new sample. • If hemoglobin decreases ≥ 3.0 g/dL from baseline and an alternative etiology is known, the subject may remain on study drug at the investigator's discretion. 
If confirmed, continue to withhold study drug until hemoglobin value returns to normal reference range or its baseline value.

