EXAM	
Investigator Assessments:
 
 • PhGA^b • SLEDAI-2K assessment • BILAG assessment • CLASI assessment • SELENA SLEDAI Flare Index Assessment 	
 • 12-lead ECG • Weight • Vital signs • Physical exam^c • TJC28/SJC28 • Skin photographs^d
LOCAL LAB	
 • Urine pregnancy test (WOCBP only)^h 	
CENTRAL LAB	
 • Complement C3 and C4 testing • anti-dsDNA • Clinical chemistry, hematology (CBC), urinalysis, UPCR • IgG and IgM • Blood samples for elsubrutinib and upadacitinib PK analysis^{i,n} 	
 • Biomarker samples: whole blood for BTK occupancy analysis (only select number of sites and subjects in the US)^{f,i} • Biomarker Sample: whole blood for BTK Y223 phosphorylation assay^{f,i} • Biomarker Sample: whole blood (plasma, serum, DNA and RNA)^{f,k,m} • Biomarker Sample: whole blood viable PBMCs^{f,m} • Biomarker Sample: whole blood: Immunophenotyping (TBNK, B cell subsets)^{f,m} • Biomarker Sample: Interferon signature^f
TREATMENT	
 • Dispense study drugⁿ 	
 • Review and copy subject dosing diary and perform drug reconciliationⁿ

 INTERVIEW	
 • AE and AESI assessment • Prior and concomitant therapy 	
 • Steroid therapy assessment • Verification of continued contraceptive measures for WOCBP
 PROs	
 • PtGA 	
 EXAM	
Investigator Assessments:
 
 • PhGA^b • SLEDAI-2K assessment • BILAG assessment • CLASI assessment • SELENA SLEDAI Flare Index Assessment 	
 • Weight • Vital signs • Physical exam^c • TJC28/SJC28 • 12-lead ECG (Week 36 only)
 LOCAL LAB	
 • Urine pregnancy test (WOCBP only)^h 	
 CENTRAL LAB	
 • Complement C3 and C4 testing • anti-dsDNA 	
 • Clinical chemistry, hematology (CBC), urinalysis, UPCR
 TREATMENT	
 • Dispense study drugⁿ 	
 • Review and copy subject dosing diary and perform drug reconciliationⁿ

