The ECGs will be evaluated by an appropriately trained physician at the site ("local reader"). The local reader from the site will sign and date all ECG tracings and will provide his/her global interpretation as a written comment on the tracing using the following categories:

- Normal ECG
- Abnormal ECG – not clinically significant
- Abnormal ECG – clinically significant

Only the local reader's evaluation of the ECG will be collected and documented in the subject's source folder. The automatic machine reading (i.e., machine-generated measurements and interpretation that are automatically printed on the ECG tracing) will not be collected.

ECGs with QT interval corrected for heart rate using Fridericia's correction formula (QTcF) should be reported (or calculated) and documented in the source documents and later transcribed on to the appropriate electronic case report form (eCRF) if QTcF prolongation is observed.

A valid QTcF cannot be calculated in subjects who have a pacemaker or supraventricular or ventricular conduction abnormalities. In cases of QTcF prolongation, the baseline QTcF will need to be entered into the appropriate eCRF for comparison as well. In addition, any clinically significant findings will be documented in the source documents and later transcribed on to the appropriate eCRF. Each signed original ECG will be monitored by the responsible site monitor and kept with a subject's source documents onsite.

Subjects can have a repeat ECG at any time during the study as warranted based on the opinion of the investigator.

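### SAP 9.6 counts QTcF above 500 msec but not the Protocol's other numeric QTcF stopping criterion, a confirmed rise of at least 60 msec; separately, its ECG visit list lacks Week 36

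*SAP*

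**What the plan says.** SAP Section 9.6 has two sentences on ECGs. The first lists the visits: "ECG is collected at Screening and Weeks 2, 4, 8, 12, 16, 20, 24 and 48". The second gives the analysis: "The number and percentage of subjects with QTcF prolongation (QTcF > 500 msec) will be summarized", by arm in the Safety Analysis Set. No other part of the SAP analyses ECG data. Section 9.1 names adverse events, laboratory values and vital signs; Section 10.0 plans nothing further; the interim safety list in 11.2.4 has no ECG item; and Appendix C sets criteria only for blood pressure and weight. Yet SAP 3.4 and Protocol 7.4 both name ECGs among the safety evaluations.

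Protocol Section 5.5 requires study drug to stop for "a confirmed absolute QTcF value > 500 msec or confirmed increase of ≥ 60 msec from Baseline". A sub-item repeats the second criterion on its own: "Subject's QTcF increases from Baseline ≥ 60 msec, the investigator will evaluate, confirm the value, and treatment should be stopped". Section 6.2, under ECG abnormality, gives the same pair, including a "confirmed increase of ≥ 60 msec from Baseline". There is also a non-numeric criterion, a clinically significant ECG change with a reasonable possibility of relation to study drug.

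On visits, Protocol Appendix D ticks a Week 36 ECG, and Operations Manual Section 2.1 agrees: "12-lead ECG (Week 36 only)". On data capture, Operations Manual Section 3.8 says: "In cases of QTcF prolongation, the baseline QTcF will need to be entered into the appropriate eCRF for comparison".

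**The concern.** The Protocol treats a 60 msec rise as sufficient by itself to stop treatment. A safety table that uses only the 500 msec threshold can show nothing for a subject whom the trial took off drug for QT. An imbalance between arms under the rise criterion would then not show in the one summary meant to describe QT. That matters most when events are few and the table is read by itself.

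The visit list raises a different question. Week 36 is the only scheduled ECG between Weeks 24 and 48. If a programmer took the list in 9.6 as the set of visits to analyse, the only scheduled check in that interval would drop out. The two points are independent: the missing Week 36 entry does not cause the missing 60 msec row.

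**Working it through.** The plan states no figure to reproduce here. The check compares the criteria and the visit lists, then asks which subjects fall between them.

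**Inputs**
- Stopping criteria: QTcF > 500 msec, or rise ≥ 60 msec, each confirmed (Protocol 5.5, 6.2).
- Tabulated criterion: QTcF > 500 msec (SAP 9.6).
- Entry limit: Screening QTcF above 480 msec is exclusionary (Protocol 5.1, criterion 27).
- Baseline: last measurement before first dose (SAP 9.1). Appendix D schedules an ECG at Screening and none at the Baseline visit, so this is normally the Screening ECG.

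**Who is not counted.** Let B be baseline QTcF. A subject meets the rise criterion and stays out of the table when

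B + 60 ≤ QTcF ≤ 500.

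This range is non-empty only if B + 60 ≤ 500, that is B ≤ 440. In whole msec:

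| Baseline B | Lowest QTcF with rise ≥ 60 | Meets the rise criterion, not in the SAP table |
|---|---|---|
| 380 | 440 | 440 to 500 |
| 400 | 460 | 460 to 500 |
| 420 | 480 | 480 to 500 |
| 440 | 500 | 500 only |
| 441 | 501 | none |
| 480 | 540 | none |

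For illustration, a change from 410 to 475 msec is a rise of 475 − 410 = 65 msec. Once confirmed, it meets the Protocol's stopping criterion; at 475 msec it is not counted under 9.6. From baseline 441 up to the entry limit of 480, any rise of 60 msec passes 500 and is counted.

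**Visits**
- Protocol, post-baseline: Weeks 2, 4, 8, 12, 16, 20, 24, 36 and 48 (the last shared with Premature Discontinuation), which is 9.
- SAP 9.6, post-baseline: Weeks 2, 4, 8, 12, 16, 20, 24 and 48, which is 8.
- The only scheduled week that differs is Week 36. The SAP list also does not name the Premature Discontinuation visit.

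**Where else a stop for a 60 msec rise would show**
- SAP 5.0 counts study drug discontinuations by primary reason, not by QTcF criterion.
- SAP 9.2.5 and 9.2.9 summarise and list AEs leading to discontinuation, which needs the change to have been recorded as an AE. Protocol 6.1 says when laboratory and vital sign changes become AEs; that rule does not name ECG changes, so recording is not assured.

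**The case against.** The best counter-case is that no promised analysis is missing. Protocol 7.4 names ECGs as a safety assessment, but its change-from-baseline summaries cover vital signs, physical examination and laboratory values. A stopping rule governs individual management, and nothing says each must have its own table. This stands: the point is an improvement to the summary, not the repair of a broken commitment.

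Four stronger readings are tempting, and the documents do not support them.

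- *Week 36 events are excluded.* The visit sentence describes collection. The sentence that defines the count has no visit restriction, so on a plain reading a Week 36 value above 500 msec is included.
- *Subjects stopped for QT vanish from the report.* They are in disposition and possibly among AEs leading to discontinuation, and an unblinded DMC reviews safety data quarterly (SAP 11.1). What is missing is a count by arm of the rise criterion.
- *Every subject with a 60 msec rise is missed.* Anyone who also passes 500 msec is counted, which includes every such subject with baseline above 440 msec. A single unconfirmed reading is not a stop at all.
- *The data are already on the eCRF.* Operations Manual 3.8 has QTcF transcribed when prolongation is observed and does not define prolongation. SAP 9.6 attaches the term to values above 500 msec. If sites read it that way, a rise to 475 msec might not be entered. Clinically significant findings are also transcribed, which helps, but capture is not guaranteed for just the subjects at issue.

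**Conclusion.** The point holds in a limited form. SAP 9.6 tabulates one of the Protocol's two numeric QTcF discontinuation criteria. Subjects stopped for a confirmed rise of at least 60 msec with QTcF at or below 500 msec, all with baseline at or below 440 msec, are not counted in the SAP's only QT summary. The number affected cannot be estimated from the documents, which give neither a baseline QTcF distribution nor an expected rate of such rises. No efficacy result depends on it.

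The Week 36 omission is a discrepancy to reconcile, not a demonstrated loss of data.

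The conclusion assumes that 9.6 is the complete ECG analysis, as the rest of the SAP indicates, and that baseline for ECG follows the general safety definition in 9.1. The change is worth making because it is small and aligns the table with the Protocol's own criteria. Appendix C already uses change-from-baseline criteria for blood pressure and weight.

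**What to change.** In SAP 9.6, summarise by arm, in the Safety Analysis Set, the count and percentage of subjects with:

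- (a) QTcF above 500 msec;
- (b) a rise of at least 60 msec from baseline, baseline being the last ECG before first dose (normally Screening);
- (c) either.

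Use all recorded post-baseline ECGs, including Week 36, Premature Discontinuation and unscheduled tracings. State whether a single reading counts or only a confirmed one, since the Protocol's criteria require confirmation. Add Week 36 and Premature Discontinuation to the visit list so that it matches Protocol Appendix D.

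The cost is two extra table rows and a corrected sentence, provided the data exist. The sponsor should first check whether a 60 msec rise that stays at or below 500 msec triggers entry of both the QTcF and its baseline on the eCRF. If it does not, either clarify the entry instruction or footnote row (b) as limited to recorded cases. Otherwise a zero in that row could reflect missing entry rather than no events. No clinical rule or efficacy analysis changes.

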10.0 Other Analyses

No other analyses are planned.

11.0 Interim Analysis

11.1 Data Monitoring Committee

An unblinded internal data monitoring committee (DMC) has been established to ensure the overall integrity and conduct of the study. DMC reviews will be conducted quarterly. In addition to the unblinded internal DMC, a multi-disciplinary internal Safety Review team will also conduct regular reviews in a blinded fashion during the study and at study completion. AbbVie will also conduct regular systematic reviews of emerging safety data from all clinical studies with elsubrutinib, upadacitinib and ABBV-599 (elsubrutinib/upadacitinib) combination.

A separate DMC charter describes the roles and responsibilities of the DMC members, frequency of data reviews, relevant data to be assessed, and general operations.

Since there are no efficacy analyses for early stopping, no alpha adjustment is needed.

11.2 Interim Analysis

An unblinded interim analysis will be performed after the first 50% of the subjects complete Week 24 visit or withdraw from the study by an independent team at AbbVie that does not include members of the blinded M19-130 Study team. The objective of the interim analysis is to reassess the treatment regimens in the rollover Study M20-186. The Interim Analysis results will be reviewed by an Internal Executive Review Committee (IERC) following a separate IERC charter and one or more treatment groups may be terminated. The IERC members are not involved in the study but have the depth of technical knowledge and experience to make decisions based on Interim Analysis results.

An interim unblinding plan will be developed separately describing the analysis to be presented to the IERC and will include execution logistics, unblinded analysis team, and the data chain of custody to protect the integrity of the clinical study.

11.2.1 Interim Analysis Population

Efficacy Analysis Population

- Full Analysis Set for Interim Analysis (FAS_IA): all randomized subjects with at least one dose of study drug before the cutoff date (20JUN2021). Subjects will be analyzed as randomized.
 - FAS_IA50 Subset: the subset of FAS_IA which includes the first 50% of planned randomized subjects.

Safety Analysis Population

- Safety Analysis Set for Interim Analysis (SA_IA) includes same subjects as FAS_IA. Subjects will be analyzed as treated.
 - SA_IA50 Subset includes same subjects as FAS_IA50 Subset. Subjects will be analyzed as treated.

Analysis of efficacy endpoints and summaries of baseline demographics and disease characteristics will be based on the FAS_IA50 Subset for primary analysis and on the FAS_IA for additional supportive analysis.

Safety analysis will be performed based on the SA_IA for primary analysis and on the SA_IA50 Subset for additional supportive analysis.

Cutoff dates for all efficacy and safety analysis are as follows:

- For subjects in FAS_IA50 Subset or SA_IA50 Subset, the cutoff date is 7JUL2021.
- For the rest of subjects, the cutoff date is 20JUN2021.

This interim analysis will also include PK and Biomarker data. PK analysis and communication plan will be provided separately by CPPM.

11.2.2 Subject Disposition, Demographics and Disease Characteristics, and Treatment Compliance

The following summaries will be provided based on FAS_IA and FAS_IA50 Subset:

- Subject disposition (randomized, took at least one dose, completed study drug at Week 24, completed study drug at Week 48, prematurely discontinued study drug, completed the 24 weeks study period, completed Week 48 Study Period, prematurely discontinued study, enrolled in LTE (M20-186)).
- Demographics and Disease Characteristics:
 - Sex (male, female).
 - Age (years).
 - Age category [18 – < 40 years old, 40 – < 65 years old, ≥ 65 years old].
 - Ethnicity (Hispanic or Latino, Not Hispanic or Latino).
 - Race (White, Black or African American, American Indian or Alaska Native, Native Hawaiian or Other Pacific Islander, Asian, Other).
 - Geographic region (North America, South/Central America, Western Europe, Eastern Europe, Asia Japan, Asia Other, Other).

- Weight (kg).
- Weight Categories (< 60 kg, ≥ 60 kg).
- Height (cm).
- Body Mass Index (BMI) (kg/m²).
- BMI Category (BMI < 25 kg/m², BMI ≥ 25 kg/m²).
- Study drug duration and compliance.

11.2.3 Efficacy Analyses

Primary Endpoint

The primary efficacy endpoint (achieving SRI-4 and steroid dose ≤ 10 mg prednisone equivalent once a day (QD) at Week 24). Will be analyzed according to the study SAP (Section 8.4) based on the FAS_IA50 Subset.

Additional analyses will also be performed for the primary endpoint at the interim analysis based on FAS_IA50 Subset: for subjects who don't have Week 24 data, all available data will be used to impute Week 24 response using multiple imputation method.

Secondary and Additional Endpoints

The following secondary and additional endpoints will be included in the interim analysis:

- Achievement of SRI-4 at all visits.
- Achievement of BICLA response at all visits.
- Achievement of ≥ 4-point decrease in SLEDAI-2K from Baseline at all visits.
- Change from Baseline in SLEDAI-2K at all visits.
- Change from Baseline in PhGA at all visits.
- Number of mild, moderate, or severe flares per patient-year (respectively and overall) by Safety of Estrogens in Lupus Erythematosus National Assessment (SELENA) SLEDAI Flare Index (SFI), assessed by number and types of flare

(mild/moderate, severe, and any) per subject through Week 24 and through Week 48.

- Achievement of at least a 50% reduction from baseline in prednisone dose at all visits.
- Achievement of SRI-4 and steroid dose ≤ 10 mg prednisone equivalent once a day (QD) at all visits starting from Week 8.
- Steroid burden, assessed as change from Baseline at all visits.
- Change from Baseline in Functional Assessment of Chronic Illness Therapy (FACIT)-Fatigue at all visits.
- Change from Baseline in Pain Numerical Rating Scale (NRS) at all visits.

Analysis specified in Section 8.5 will be performed.

